b. Treatment History and Utilization. There are two participant scenarios with respect to treatment history. One scenario is youth may have received subsequent psychosocial or medication treatment following their failure in the CBT protocol in R01 MH079943. The second scenario is youth may be currently receiving a medication treatment (youth currently involved in other psychosocial treatments will be excluded). Each scenario will be assessed carefully via questions¹⁴⁶ to be completed by parents at each of the three assessment sessions. This will ensure we identify past treatment, current additional treatment, and new additional treatment families may start during their participation in the R34. Responses will be collapsed to reflect three treatment variables: past medication, past psychotherapy, and current medication. If any of these treatment history and utilization variables are significantly associated with R34 condition, we will include them as covariates in analyses and will draw our conclusions accordingly.

INNOVATION

[As noted in the critiques of our initial submission, the proposed project is innovative in the following ways:

- ABMT is a theoretically-grounded intervention that targets subcortical, automatic processing of anxiety that may address brain regions and processes that are less directly impacted by CBT.
- This is the first trial of this brief intervention for an impacted population that at present has few evidence-based alternatives for their anxiety disorders should they fail to respond to CBT.
- ABMT is potentially more cost-efficient (shorter, requires less skilled therapists) and more disseminable (can be conducted at home, provide access where experts are not available) than traditional talk therapies. It may also be acceptable to those who find medication or talk therapy unacceptable.
- Addressing CBT nonresponse with a non-linguistic computer-based intervention is innovative compared to

the “more of the same” approach (booster sessions, augmented by medication).

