Task. This aim represents the efficacy test of the proposed project. The traditional ordinary least squares (OLS) analysis is a two group single degree of freedom contrast between patients in the ABMT condition (n=35) and patients in the PC Task condition (n=35) using pre scores as a covariate to increase statistical power. The single degree of freedom contrast focuses on the comparison of adjusted means at post. Of interest is whether the contrast between conditions is statistically significant for IE ratings of youth anxiety severity (PARS; **Hypothesis 1a**), parent ratings on youth’s anxiety symptoms (SCARED-P; **Hypothesis 1b**), and youth self ratings on anxiety symptoms (SCARED-C; **Hypothesis 1c**). Significantly lower scores in the ABMT condition as compared to the PC Task would support the efficacy of ABMT for CBT nonresponders. The robust counterparts of these contrasts are described in Wilcox¹⁴⁹. The two recommended methods focus on either medians or 20% trimmed means in conjunction with smoothers to model the regression surface for the covariates. We thus will pursue traditional analyses of means as well as robust analyses of medians and trimmed means, giving analytic preference to the latter methods over the more traditional OLS estimates, based on the simulation results of Wilcox¹⁴⁹.

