Aim 2: Examine whether ABMT, as compared to PC Task, leads to significantly lower levels of anxiety at an eight week FU. This aim represents a test of the maintenance of ABMT effects over eight weeks. The analysis will focus on the between-groups contrast between patients in the ABMT condition (n=35) and patients in the PC Task condition (n=35). Patients’ mean scores on the FU measures will be contrasted using a single degree of freedom contrast as a function of condition (ABMT, PC Task) in a between-groups design with the pre scores as a covariate. The single degree of freedom contrast focuses on the comparison of adjusted means at FU. Of interest is whether the contrast between conditions is statistically significant for IE ratings of youth anxiety severity (PARS; **Hypothesis 2a**), parent ratings on youth’s anxiety symptoms (SCARED-P; **Hypothesis 2b**), and youth self ratings on anxiety symptoms (SCARED-C; **Hypothesis 2c**). Significantly lower scores in the ABMT condition as compared to the PC Task would demonstrate that ABMT produces reductions in anxiety at least eight weeks after treatment has ended. The robust counterparts of these contrasts are those described for Aim 1¹⁴⁹.

Aim 3: Gain perspective on the viability of variables as potential mediators and moderator of ABMT (Figure 2). This aim represents an exploratory aspect of this R34 application that will lay the groundwork for a larger R01, which may include testing of the mediators and moderator of ABMT’s anxiety reduction effect. As

Aim	Contrast	Outcomes
Aim 1: Efficacy	ABMT vs. PC Task at Posttreatment	PARS, SCARED-C/P
Aim 2: Maintenance	ABMT vs. PC Task at Follow up	PARS, SCARED-C/P
Aim 3: Potential Moderator & Mediators	1. ABMT vs. PC Task at Posttreatment (immediate effect) 2. ABMT vs. PC Task at Follow up (maintenance effect)	Attention Bias & Interpretation Bias (mediators), Attention Control (moderator)

Table 2. Planned Analyses.

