Approaches to increasing statistical power in randomized clinical trials generally focus on increasing sample size, but an alternative strategy is to introduce covariates that reduce within-subject error and thereby increase the precision of estimated between-group differences. The latter approach leads to a more sensitive significance test for the treatment effect¹⁵⁷. In the proposed R34, our sample size will be constrained by the number of youth who do not respond to CBT in the current R01 MH079943 study. Thus, we will increase the statistical power available by adjusting for relevant covariates measured at pre. Covariate adjustment for the pre score on each outcome measure will substantially increase statistical power¹⁵⁸. For example, if pre and post scores correlate at $r=.65$ (which seems reasonable based on the test-retest reliability estimates for our outcome measures and preliminary pre to post data from R01 MH079943), then power of 0.80 to detect a mean difference of $d=.50$ is available with a sample size of approximately 36 per group. Our projected sample size of 35 per group maps closely onto this estimate. To increase statistical power further, we will covary [pre attention bias scores] and examine other characteristics measured at pre (e.g., age, gender, diagnosis, R01 MH079943 condition, past treatment, current medication use, number of comorbid diagnoses) to determine whether they differ across conditions. If they vary across conditions, we will include them as covariates which will reduce the "noise" in the estimated treatment effect and thereby increase power. In general, the robust methods of analysis will be as powerful or more powerful than the least squares regression methods, so the power estimates above apply, conservatively, to the robust methods of analysis as well.

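### Entering further baseline covariates only when they differ between arms does not, on average, raise power as the Statistical Power section says; the effect is small and the fix is a fixed covariate set

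*Combined protocol and SAP*

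**What the plan says.** Two covariates are unconditional. Aim 1 compares adjusted post means "using pre scores as a covariate to increase statistical power", and Aim 2 compares FU means "in a between-groups design with the pre scores as a covariate". The Statistical Power section adds a second: "we will covary [pre attention bias scores] and examine other characteristics measured at pre".

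The other characteristics are conditional. Statistical Power names seven as examples (age, gender, diagnosis, R01 condition, past treatment, current medication, comorbidity count) and looks at them up to "number of comorbid diagnoses) to determine whether they differ across conditions". It continues: "If they vary across conditions, we will include them as covariates", on the ground that this reduces noise "in the estimated treatment effect and thereby increase power". No threshold is given and the list is open.

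Three other places set related rules:
- Measures, V.b, Treatment History and Utilization: "If any of these treatment history and utilization variables are significantly associated with R34 condition, we will include them as covariates in analyses". This covers variables that overlap with the Statistical Power list, uses a significance criterion without a level, and makes no power claim.
- Research Overview and Future Plans: R01 condition is a covariate where judged appropriate.
- Preliminary Studies, after Table 1: time since the R01 and intervening treatment are covariates on the same discretionary basis.

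The opening of Data Analysis also plans comparisons of baseline variables by condition, to check the randomization.

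**The concern.** Covariate adjustment gains precision when the covariate predicts outcome. Statistical Power itself gives this reason for adjusting, then selects the further covariates on something else: whether they differ between arms. In a randomized trial that difference is chance. A strongly prognostic variable that happens to be balanced is left out, although adjusting for it would help. A variable unrelated to outcome that happens to be imbalanced is put in, where it costs precision.

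Two things are at stake. The sample cannot be enlarged, because it is capped by the number of R01 nonresponders, so a real power gain from covariates would be worth having. And the covariate set of the primary contrast stays open until the arms have been compared, under triggers worded differently in four places, so two analysts could fit different models.

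**Working it through.** **Inputs from the plan.** d=.50 (Statistical Power); pre-post r=.65 (same); 35 per arm (Aim 1); seven named candidates. Two-sided alpha .05 is stated for Aim 3 and assumed here for Aim 1.

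**Inputs assumed, because the plan gives none.** The screening level (p<.05, with .10 and .20 as alternatives), the number of prognostic candidates, their partial correlation with outcome given the pre score (0 to .5), and independence of the candidates.

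**The plan's own figure.** Unadjusted n per arm = 2(1.960+0.842)²/.50² = 62.8, so 63 by the normal formula; the plan says 64. With the pre score the variance factor is 1-.65² = .5775, and 62.8 × .5775 = 36.3; the plan says about 36. At 35 per arm the power is .786 (normal) or .774 (t). The plan's figure is reproduced, and the conditional covariates play no part in it.

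**Why imbalance is the wrong criterion.** Let ρ be the partial correlation of a covariate with outcome and q its sample correlation with arm. Adding it multiplies the variance of the treatment estimate by about (1-ρ²)/(1-q²). Randomization makes q unrelated to ρ. With 70 patients, p<.05 means |t| > 1.995 on 68 df, so q² > 3.98/(3.98+68) = .055. A covariate admitted by the rule therefore improves precision only if ρ² exceeds .055, that is |ρ| above about .235.

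**Simulated change in power (percentage points).** OLS ANCOVA, pre score and pre attention bias always in, base power about .76, p<.05 screen. In the seven-candidate column one candidate is prognostic.

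| Partial r | Rule, 1 candidate | Rule, 7 candidates | Always enter that one covariate |
|---|---|---|---|
| 0 | -0.2 | -1.4 | -0.7 |
| .2 | -0.1 | -0.9 | +0.9 |
| .3 | +0.2 | -0.8 | +3.3 |
| .5 | +1.0 | -0.1 | about +10 |

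**Where the average comes from.** With one candidate the rule fires in about 5% of trials. In those trials:
- At partial r 0, power goes from .745 to .706, and .05 × (-3.9) = -0.2 points.
- At partial r .3, it goes from .720 to .765, and .05 × 4.5 = +0.2.
- At partial r .5, it goes from about .69 to .87, and .05 × 18 = +0.9. This pair rests on few trials; across runs it lay between .65 and .69 without the covariate and between .83 and .87 with it.

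**Sensitivity.**
- Looser screens widen the range: -1.9 to +1.8 at p<.10 and -3.0 to +3.4 at p<.20. The upper ends need a single candidate with partial r .5.
- Several prognostic candidates move the result towards zero or slightly above. Three of seven at .3 give -0.1 (p<.05) and +0.1 (p<.20); all seven at .2 give +1.3 (p<.20).
- If pre attention bias is itself prognostic (assumed partial r .3), base power is .80 and the change at p<.05 is -1.2 to +0.2.
- At 31 per arm, within the plan's expected 60-66 completers, and with only the pre score always in, the change at p<.05 runs from -1.5 (seven candidates, none prognostic) to +1.1 (one candidate explaining 30% of the remaining variance).

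**How often the model changes.** With seven independent candidates, at least one enters with probability 1-.95⁷ = .30 at p<.05, 1-.90⁷ = .52 at p<.10 and 1-.80⁷ = .79 at p<.20. Independence matters: at an assumed correlation of .5 the first figure is about .23.

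**Validity.** With pre attention bias always in, rejection under the null was .038 to .050 and the mean estimate was -.497 to -.503 against a true -.50.

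**The case against.** The strongest reply is that the sentence is true where it matters. If the covariate that differs is clearly prognostic, adjusting for it recovers a good deal of power in that trial. This stands. But it happens in about one trial in twenty per candidate at p<.05, and nothing in the rule favours prognostic variables, so it does not support a general claim.

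A second reply is that little depends on the sentence. This also stands. The further covariates are offered as an extra, without a figure, after the sample size has been justified by the pre score alone.

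Third, the fix can cost more than the rule: one fixed covariate unrelated to outcome loses about 0.7 points, against 0.2 under the rule with one candidate. The plan's own review of predictors of CBT nonresponse reports null or inconsistent findings. That is a reason to add none unless one is supported, not a reason to select on imbalance.

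Fourth, Aim 1 describes medians and trimmed means as well as OLS, "giving analytic preference to the latter methods over the more traditional OLS estimates". Those methods were not simulated, so the figures describe the OLS contrast only. The principle, that chance imbalance is uninformative about prognosis, does not depend on the estimator.

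A reader might go further and infer that the rule biases the treatment effect, inflates type I error or undermines the sample size. The checks show none of these. Nor should one infer that the rule reliably loses power: the negative seven-candidate figures rest partly on assuming independent candidates with at most one prognostic.

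**Conclusion.** The stated power benefit is wrong as a general statement. Under the assumptions given (OLS ANCOVA, 35 per arm, d=.50, r=.65, p<.05 screen, independent candidates, at most one prognostic) the average change is about -1.4 to +1.0 points: little or no gain. The sign depends on how many candidates are prognostic and how strongly, neither of which the plan gives.

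The trigger is also undefined, so the covariate set of the primary contrast is not fixed in advance. The V.b rule shares that second problem but not the first, since it claims no gain in power.

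This is a minor point. The unconditional adjustment for the pre score and pre attention bias is sound and untouched by it.

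**What to change.** Before unblinding, replace the imbalance and discretionary triggers in Statistical Power, Measures V.b, Research Overview and Future Plans, and Preliminary Studies with one covariate set for the primary contrast, entered regardless of balance:
- the outcome's pre score;
- pre attention bias;
- at most one or two further pre-assessment covariates chosen for expected relation to outcome, and none if none is supported.

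R01 data could inform the choice, with the caution that 70.4% of its completers were responders, so relations may not carry over to nonresponders. State that pre-assessment values are meant, because the treatment questions in V.b are asked at all three assessments.

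Delete the statement that adjusting for covariates that vary across conditions increases power. Keep the baseline comparisons in V.b and at the start of Data Analysis as descriptive, and report any adjustment for chance imbalance as a labelled sensitivity analysis.

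The cost is wording in four places, one degree of freedom per added covariate, and up to about 0.7 points of power for each one that turns out not to be prognostic. The possible gain from one covariate is about 1 point at partial r .2 and about 3 at .3.

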We appreciate these positive comments about how the project is innovative. In addition, in response to reviewers’ request that we further develop a theory-treatment link, in this resubmission we have further developed this link regarding why some patients do not respond to CBT and why ABMT is likely to help those patients. The innovation of the project has been further enhanced by including attention control as a potential moderator of ABMT’s anxiety reduction effect. This project moves beyond past ABMT studies by collecting data not just on outcome, but also potentially promising mediator and moderator variables contained in our model.]

DATA ANALYSIS

Data management protocols will be used to ensure integrity of the data. Data will be checked for out of range and missing values. Missing data should be minimal. Missing values will be estimated using Markov chain Monte Carlo multiple imputation algorithms based on the Gibbs sampler in the Mplus program¹⁴⁷. Space constraints do not permit us to describe all the details of our analytic approach. We highlight major issues focusing on the Specific Aims. Primary methods of analysis will focus on traditional least squares tests of means as well as modern robust estimation procedures¹⁴⁸ that are outlier resistant, make minimal assumptions about population distributions, and are more powerful than traditional methods¹⁴⁸⁻¹⁵⁰. The latter techniques rely on Wilcox’s R routines¹⁴⁹. Initial analyses will examine associations between condition and baseline variables (i.e., diagnosis, treatment history, demographics, and time since R01 MH079943 FU) to ensure randomization was successful. Table 2 provides a summary of planned analyses. We will compare the robustness of our conclusions with and without statistical corrections for multiple tests¹⁵¹. We will use a Holm adjusted modified Bonferroni method for controlling experimentwise error rates; it is more powerful than traditional Bonferroni or Scheffe methods¹⁵².

Findings on acceptability, feasibility, and maintenance of blind variables will be reported separately for ABMT and PC, as well as the total sample. We will test for differences between ABMT and PC on these variables using independent sample t-tests.

Aim 1: Test whether ABMT produces significantly lower levels of anxiety at post as compared to PC

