Past research on ABMT with adult clinical samples has reported medium to large effect sizes for reductions in anxiety symptoms (Hedge's $d=.78$) and large effect sizes for reductions in attention bias toward threatening stimuli (Hedge's $d=1.16$)³². The extent to which similar effect sizes would be found in the proposed sample of youth who did not respond well to CBT is unknown. In this project, we would like to be able to detect effects of medium size (Cohen's $d=.50$) or larger. For a single degree of freedom contrast between two independent groups, the approximate sample size needed to achieve power of 0.80 for a mean difference of $d=.50$ is 64 per group, a number that exceeds our projected $n=35$ per group.

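### Least-squares power is carried over as conservative to the preferred robust analyses, but under the plan's own normal model it is optimistic, and no single primary estimator is named

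*Combined protocol and SAP*

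**What the plan says.** The Statistical Power section sets its target: "we would like to be able to detect effects of medium size (Cohen's $d=.50$) or larger". For an unadjusted two-group contrast it says "the approximate sample size needed to achieve power of 0.80 for a mean difference of $d=.50$ is 64 per group". With the pre score as covariate and a pre-post correlation of .65 it arrives at about 36 per group, and adds: "Our projected sample size of 35 per group maps closely onto this estimate".

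The analysis to which this power is meant to apply is described under Data Analysis, Aim 1. Three estimators will be run: "We thus will pursue traditional analyses of means as well as robust analyses of medians and trimmed means", the trimmed means being 20% trimmed and both robust versions using smoothers for the covariates. The robust versions rank first, "giving analytic preference to the latter methods over the more traditional OLS estimates". Aim 2 refers back to the same robust methods for the follow-up contrast.

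Two statements connect the power figures to the robust methods. The opening of Data Analysis says that these methods "make minimal assumptions about population distributions, and are more powerful than traditional methods". The Statistical Power section claims at least equal power for them as a general rule, and draws this inference for its own figures: "so the power estimates above apply, conservatively, to the robust methods of analysis as well".

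**The concern.** The sample sizes are least-squares figures, while the preferred analysis is not least squares. Whether a trimmed mean or a median has more or less power than the mean depends on the error distribution. When errors are normal, both have less. Calling the least-squares figure conservative promises a lower bound, yet the plan gives neither a PARS distribution nor a robust power calculation to support one.

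Aim 1 is presented as the trial's efficacy test, and its size is limited by how many CBT nonresponders the parent trial yields. A shortfall therefore cannot easily be met by recruiting more. If errors are near normal, the preferred primary test has less power than the plan reports.

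Separately, robust methods are ranked above OLS only as a class. Nothing says whether the median or the trimmed mean decides Hypothesis 1a, and the gap carries over to 2a. The two can give different answers on the same data.

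**Working it through.** **Inputs.** From Statistical Power: d = 0.50, target power .80, r = .65, 35 per group. From Aim 1: OLS, 20% trimmed mean, median. From Preliminary Studies: 63 expected completers. Two-sided alpha of .05 is stated only for Aim 3. It is assumed here because it reproduces the plan's figures; a one-sided test gives 29 per group and does not.

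**Step 1: reproduce the plan's figures.**
- Unadjusted: n = 2(1.960 + 0.842)² / 0.50² = 62.8, so 63 per group by the normal formula; the t test gives 64 (power .801). Stated: 64.
- Adjusted: 62.8 × (1 − .65²) = 62.8 × .5775 = 36.3, so 37 per group. Stated: about 36.
- Power at 35 per group: residual SD = √.5775 = .760; 0.50 / (.760 × √(2/35)) = 2.752; Φ(2.752 − 1.960) = .786 (.774 with the t distribution).

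The plan's figures are thus normal-theory least-squares figures.

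**Step 2: same model, robust estimators.** Efficiency relative to the mean under normality is .874 for the 20% trimmed mean and 2/π = .637 for the median.
- Trimmed mean: 2.752 × √.874 = 2.573; power Φ(0.613) = .730; n for .80 = 36.3/.874, so 42 per group.
- Median: 2.752 × √.637 = 2.196; power Φ(0.236) = .593; n for .80 = 36.3/.637, so 57 per group.

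**Step 3: simulation, d = .50, r = .65.** The tests were the OLS ANCOVA t test, Yuen's 20% trimmed test, and median tests by order-statistic standard error and by percentile bootstrap. Ranges for the median mostly reflect these two tests. There are 35 per arm unless stated, and errors have equal variance across distributions.

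| Errors | OLS | 20% trimmed | Median |
|---|---|---|---|
| Normal | .77 | .71 | .50–.57 |
| Normal, 63 completers | .72 | .66 | .50–.52 |
| Normal, LOWESS adjustment | .78 | .73 | .54–.59 |
| Normal, pre attention bias explains a further 5–10% of variance (assumed) | .80–.84 | .75–.79 | .56–.65 |
| Uniform | .76–.77 | .52–.54 | .35 |
| Moderately skewed gamma | .77 | .76 | .55–.62 |
| t(8) | .76 | .78 | .59–.65 |
| t(5) | .77 | .84 | .66–.73 |
| 10% contamination, SD ×3 | .78 | .87 | .70–.75 |
| Laplace | .78 | .89 | .84–.85 |
| t(3) | .80–.82 | .96 | .86–.91 |
| 10% contamination, SD ×5 | .79 | .98 | .95 |

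The main scenarios used 8,000 runs (Monte Carlo standard error √(.77 × .23 / 8000) = .005); the LOWESS and extra-covariate rows used 4,000. Except in the LOWESS row, the pre score was adjusted linearly or its slope taken as known. By simulation under normality, n per arm for .80 is about 37–38 for OLS, 42 for the trimmed mean and 58–62 for the median.

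**Step 4: is the median loss only a matter of test size?** Both median tests are undersized at 35 per arm (null rate .033–.037, normal). After size adjustment, power is OLS .76, trimmed .69, median .56–.62 under normality, and .79, .83, .74–.78 under t(5). The ordering under normality stands.

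**Step 5: the open choice of estimator.** Under normality at d = .50, the trimmed-mean and median tests disagree on significance in 16–22% of trials. Under the null, rejection by either robust test occurs in 5.9–7.0% of trials, and by any of the three tests in 7.5–8.5%.

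**The case against.** The plan qualifies its claim as a general one and adopts robust methods to guard against outliers. Exact normality is therefore an unfavourable place to test it. With tails as heavy as Laplace, t(3) or strong contamination, even the median beats OLS. This stands: the plan's statement is not false for every distribution, and the loss for the median applies to normal, light-tailed, moderately skewed and mildly heavy-tailed errors. But a claim of conservatism needs a distribution behind it, and none is given. PARS is a bounded 0–35 total, so very heavy tails cannot be taken for granted.

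The exact smoother-based procedures were not reproduced, and ties in an integer score were not modelled. This too stands as a limit on precision. A LOWESS version left the ordering unchanged. The lower end of the median range is also sensitive to the discreteness of the order-statistic standard error: moving from 35 to 36 per arm lifts that test from .50 to .58. The median figure is best read as roughly .5 to .6.

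The inflated null rates presuppose that any positive robust test would count, and the plan states no such rule. They show what an unmade choice could cost; they are not an error rate of the plan. Part of the disagreement between the two tests reflects the lower power of the median test.

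Finally, this is a pilot, and the robust-power sentence did not set the sample size. That limits the consequence, but the sentence is still the only power statement for the preferred analysis.

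**Conclusion.** The concern holds. Under the normal model that reproduces the plan's 64 and about 36 per group, OLS power at 35 per arm is an upper figure for the robust methods. The loss is about 6 points for the 20% trimmed mean (.77 to .71) and about 20 to 27 points for the median (.77 to .50–.57). With mildly heavy tails the trimmed mean matches or exceeds OLS while the median stays below it; with much heavier tails both exceed it. The claim of conservatism is therefore not guaranteed, and it is least safe for the median.

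The missing choice between median and trimmed mean for Hypotheses 1a and 2a is a second, separate gap. These conclusions rest on two-sided alpha of .05, d = .50, r = .65 and equal residual variance across distributions. Confidence is high for the normal-model result. For PARS itself the direction is unknown, because the documents do not describe its distribution.

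**What to change.** - In Aim 1, name one estimator as the primary analysis of PARS at post (Hypothesis 1a), with the planned pre-score and pre attention bias covariates. Do the same in Aim 2 for Hypothesis 2a. Label the other estimators sensitivity analyses. The 20% trimmed mean keeps the robust preference at the smaller power cost; OLS ANCOVA is also acceptable.
- In Statistical Power, delete *conservatively* and state power for the chosen estimator under a stated distribution. For normal errors, 35 per arm and the pre-score covariate only, this is about .77 for OLS, .71 for the trimmed mean and .5 to .6 for the median.
- In the opening of Data Analysis, qualify the statement that robust methods have more power as depending on the distribution.

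The cost is wording only; every planned analysis is still run and enrolment is unaffected. The drawback is a less favourable stated power if a robust method is primary, or less protection against outliers in the primary test if OLS is chosen.
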